#### 13.2 Study Design/Endpoints

13.2.1 Primary Endpoints

Phase 1. The occurrence of a DLT as defined in section 5.3. Phase 2. The occurrence of a DLT as defined in section 5.3.

#### 13.2.2 Secondary Endpoints

Leukemia-free survival: The time from transplant to the first occurrence of an event (leukemic relapse [section 11.2] or death from any cause), or censored on date of last contact, if no event occurs.

Overall survival: The time from transplant to death from any cause, or censored on date of last contact, if no death occurs. **Cause of death will be classified according to CIBMTR consensus criteria**.

Non-relapse mortality: The time from transplant to death while in continuous complete remission, or censored on date of last contact, if no death occurs.

Relapse: The time to leukemic relapse.

Oral and gastrointestinal mucositis endpoint. The occurrence and severity of oral or gastrointestinal mucositis (between day 0 and post-transplant day 14) as graded by CTCAEv5.0.

Neutrophil engraftment: time to the first of 3 consecutive days following the nadir that the absolute neutrophil count is at least  $500/\mu$ l.

Platelet engraftment: time to the first day following the nadir that the platelet count is at least  $20,000/\mu$ l without a transfusion in the preceding 7 days.

Mucosal barrier injury-associated laboratory-confirmed bloodstream infection (MBI-LCBI) : cumulative incidence of MBI-LCBI by Day +30.

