#### 1.4 Secondary Objectives

- 1) To describe the pharmacokinetics of uproleselan in pediatric patients receiving myeloablative, busulfan based pre-transplant conditioning (this will encompass both phase 1 and phase 2).
- 2) To describe the preliminary efficacy of uproleselan by estimating the 12-month leukemia-free survival (LFS), overall survival (OS), and relapse in patients receiving uproleselan at the RP2D
- 3) To describe the maximal severity of oral and gastrointestinal mucositis in patients receiving uproleselan at the RP2D.

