# 2.4 Rationale

This phase 1/2 trial will allow us to prepare for a full-scale clinical trial, open to patients with chemo-sensitive as well as chemo-resistant AML and to patients receiving a wider variety of donor/graft types and forms of conditioning and GVHD prophylaxis. We anticipate that in the full-scale clinical trial, patients with chemo-sensitive disease will be assigned to a randomized stratum (uproleselan vs. placebo), while patients with chemo-resistant disease will be non-randomly assigned to treatment with uproleselan.

Eligibility: Eligibility for the trial will be limited to those patients at highest risk for relapse: those transplanted with refractory disease (not in remission) or transplanted in a complete remission, but with measurable residual disease on marrow testing by multidimensional flow cytometry (MRD positive). The risk of relapse associated with pre-transplant MRD approaches that associated with refractory disease. A large analysis of children and adults transplanted for AML in first or second complete remission (CR1 or CR2) showed that patients with any level of MRD pre-transplant had a nearly five-fold higher risk of relapse at 3 years compared to those who were MRD negative. Importantly, pre-transplant MRD obviated the significance of traditional risk factors, including cytogenetic risk and remission number. Similar results were shown in a pediatric only cohort in the Pediatric Blood and Marrow Transplant Consortium study ONC001 for patients receiving allo-HSCT in CR1 or CR2. The 2-year cumulative incidence of

relapse was 32% for the 113 patients who were MRD negative prior to HSCT as compared to 70% for the 10 patients who were MRD pos. (p=0.01). In both of these studies, most of the relapses in patients who had pre-HSCT MRD occurred by 6 months. In both studies, relapse-free survival for MRD positive patients was approximately 40% at 6 months.

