#### 3.1.5 **Disease status:**

Multidimensional flow cytometry (MDF) to assess disease status for eligibility will be performed centrally by Hematologics.

- In a first or second complete remission (defined as marrow with ≤1% leukemic blasts by MDF and no evidence of extramedullary disease) with minimal residual disease (MRD, defined as marrow with ≥0.05% leukemic blasts by MDF) after at least 2 cycles of induction/re-induction chemotherapy.
- Have newly diagnosed disease or disease in first relapse that is refractory (defined as marrow with >1% leukemic blasts by MDF or persistence of extramedullary disease) to at least 2 cycles of induction/re-induction chemotherapy.

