# **11. MEASUREMENT OF EFFECT**

#### **11.1 Refractory Disease**

Applies to patients who were not in remission at the time of transplant.

At Day +30 (+/-5 days) post-transplant disease evaluation, there is persistence of >1% leukemic blasts by multidimensional flow cytometry (MDF) or there is persistence of EMD.

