## 11.2 Leukemic Relapse

Applies to patients who were in remission at the time of transplant and pateints not in remission at the time of transplant who achieve remission post-transplant (based on day +30 assessment)

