# 11.3 Extramedullary Relapse

Defined as radiographic or biopsy proven extramedullary disease after documented CR or evidence of CSF recurrence.

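### The leukemia-free survival event leaves out leukemia that persists at Day +30, so a refractory patient who does not clear counts as leukemia-free until death

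*Protocol*

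**What the plan says.** Section 13.2.2 gives the LFS event as "The time from transplant to the first occurrence of an event (leukemic relapse [section 11.2] or death from any cause"; a patient without an event is censored at last contact.

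The section it cites, 11.2, limits itself to two groups: patients in remission at transplant, and "pateints not in remission at the time of transplant who achieve remission post-transplant (based on day +30 assessment").

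Persistent disease is defined separately. Under 11.1, a patient not in remission at transplant has refractory disease if, at the Day +30 (±5 days) evaluation, "there is persistence of >1% leukemic blasts by multidimensional flow cytometry (MDF) or there is persistence of EMD". The LFS definition does not cite 11.1, and neither does any other endpoint in 13.2.2.

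These patients are a planned part of the trial. Section 2.4 names the target population as "those transplanted with refractory disease (not in remission) or transplanted in a complete remission" with measurable residual disease (MRD). Section 3.1.5 admits patients who "Have newly diagnosed disease or disease in first relapse that is refractory (defined as marrow with >1% leukemic blasts by MDF" or by persistent extramedullary disease) after at least two cycles.

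Secondary objective 2 in section 1.4 includes "estimating the 12-month leukemia-free survival (LFS), overall survival (OS), and relapse in patients receiving uproleselan at the RP2D". Section 13.7 estimates 1-year LFS by Kaplan-Meier in the RP2D cohort. Section 13.8 relates 1-year LFS status (yes/no) to E-selectin ligand expression and to ST3GAL4/FUT7 expression.

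**The concern.** A patient whose leukemia was never cleared is a treatment failure on any ordinary meaning of leukemia-free survival. Under the rule as written, that patient stays on the LFS curve as event-free until death. This is a definition the protocol fixes by citing a section, not a detail it leaves open.

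Two results are exposed. One is the 1-year LFS, the first efficacy estimate named in secondary objective 2. The other is the set of biomarker summaries in 13.8, where a living patient with persistent leukemia could be entered as an LFS success, which blurs the relation between E-selectin ligand and outcome that the trial wants to explore.

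**Working it through.** **Step 1: which patients have an LFS event, and when.**

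| Patient | 11.1 | 11.2 | LFS event under 13.2.2 |
|---|---|---|---|
| In remission with MRD at transplant, later marrow relapse | not applicable | applies | relapse or death |
| Not in remission at transplant, remission at Day +30, later marrow relapse | not met | applies | relapse or death |
| Not in remission at transplant, leukemia persists at Day +30 | met | does not apply | death only |

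**Step 2: does anything else close the gap?**

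- Section 11.3 does not. The LFS definition does not cite it, and it reads "Defined as radiographic or biopsy proven extramedullary disease after documented CR or evidence of CSF recurrence", so its radiographic and biopsy route presupposes a remission.
- Section 13.1.2 does not remove these patients: one dose of uproleselan at the RP2D makes a patient evaluable for efficacy.
- Sections 5.5 and 5.6 keep them under observation: a patient off protocol therapy stays on study, and follow-up runs to 2 years.

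No other section makes 11.1 disease an LFS event.

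**Step 3: size.** The protocol states no expected LFS, so there is no figure of its own to reproduce. The one input it gives is N = 20 evaluable patients at the RP2D (13.3).

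With complete follow-up, Kaplan-Meier equals the simple proportion. If k patients with 11.1 disease are alive at 12 months, with no remission credited,

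LFS as written − LFS with 11.1 counted = k/20,

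which is 5 points for k = 1 and 0 for k = 0.

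To see what happens otherwise, assume (for illustration, not from the protocol) 8 patients event-free at 12 months, 11 other failures, and one patient with 11.1 disease at Day +30. Counting that patient as an event at Day +30 gives 8/20 = 40.0%. As written:

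- *Alive and followed to 12 months:* 9/20 = 45.0%, a rise of 5.0 points.
- *Dies at month 8:* 8/20 = 40.0%, no change at 12 months. Only the curve between Day +30 and month 8 is too high.
- *Lost to follow-up alive after j of the 11 other failures:* the curve is (20 − j)/20 just before the loss; afterwards 19 − j patients remain at risk, of whom 8 stay event-free. So LFS = [(20 − j)/20] × [8/(19 − j)].
  - j = 0: 8/19 = 42.1% (+2.1)
  - j = 5: (15/20) × (8/14) = 42.9% (+2.9)
  - j = 11: (9/20) × (8/8) = 45.0% (+5.0)

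**Step 4: when other patients are censored.** Assume instead that the 11.1 patient dies at month 8, five others are lost alive at month 4, and the remaining 14 are event-free at 12 months.

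- Event at Day +30: 19/20 = 95.0%.
- As written: the death falls when 20 − 5 = 15 are at risk, so 14/15 = 93.3%.

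The difference is −1.7 points. Moving an event later, past other patients' censoring, can therefore lower the estimate.

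**The case against.** The strongest case on the other side has four parts.

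*Nothing depends on LFS.* It is a preliminary, descriptive secondary endpoint, and its use in 13.8 is exploratory. No sample size, dose decision, TRM rule or RRT rule uses it. This stands, and it limits the weight of the point.

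*The effect is hypothetical and small beside the noise.* At 8/20 the binomial standard error is √(0.4 × 0.6/20) = 0.110, about 11 points, against 5 points for one patient. This also stands. But sampling error is reported with the estimate, whereas a misclassified patient is not visible in it.

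*A reader might infer that the error can only inflate LFS.* The documents do not support that. The last-contact censoring rule allows the downward shift in Step 4. The upward direction holds for 11.1 patients who are alive at 12 months or lost alive before then.

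*Related conventions belong in a SAP.* A death with 11.1 disease is an LFS event but is neither an 11.2 relapse nor non-relapse mortality, defined as "The time from transplant to death while in continuous complete remission". A reader might take this as a further error. It is not shown to be one: the protocol does not say that relapse and non-relapse mortality must add up to LFS failure, and it refers cause of death to CIBMTR consensus criteria. How such deaths are labelled, and how a remission first seen after Day +30 is handled, can be settled in a SAP.

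None of this removes the core gap, because the event definition itself is stated in the protocol and excludes 11.1 disease.

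**Conclusion.** The point holds as a wrong stated rule for one eligible group. It does not affect MRD-positive patients transplanted in remission, whom 11.2 covers.

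With N = 20 and complete follow-up, each patient with persistent leukemia who is alive at 12 months adds 5 points to 1-year LFS, and one who dies by 12 months adds nothing. With incomplete follow-up the net error can go in either direction. The protocol gives neither the expected share of refractory patients nor a Day +30 persistence rate, so the number affected cannot be predicted and may be zero. It would be wrong to conclude that the reported LFS will be inflated by a known amount, or that any safety decision is affected.

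Read literally, the citation of 11.2 alone also omits extramedullary and CNS relapse in 11.3. That is probably a numbering slip.

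**What to change.** In 13.2.2, define the LFS event as the first of:

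- persistent or refractory disease per 11.1, with a stated event date (for example, the Day +30 re-evaluation that shows it);
- relapse per 11.2 or 11.3;
- death from any cause.

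Use the same definition for 1-year LFS status in 13.8. This is best done before LFS outcomes are known.

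The cost is a wording change. The Day +30 marrow and extramedullary re-evaluation is already required (10.2.4), so no new data are needed to apply 11.1.

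There is a downside. LFS may come out less favourable, and a patient who first clears disease after Day +30 counts as a failure unless the SAP states a late-remission convention. Such a convention would rest on uneven data: after Day +30 the study calendar schedules no further disease re-evaluation, and relapse is assessed per institutional guidelines (10.3.6).

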11.2.1 Bone Marrow Relapse

Defined in accordance with the Children's Oncology Group's AAML1831 trial protocol criteria:

A single bone marrow sample (aspirate or biopsy) showing  $\geq$ 5% leukemic blasts confirmed by flow cytometry, FISH testing, ICH, or other molecular method.

OR

A single bone marrow sample with at least two tests showing  $\geq 1\%$  leukemic blasts.

Examples of tests include:

- Flow cytometry showing leukemia  $\geq 1\%$  by multidimensional flow cytometry (MDF) in a CLIA-approved laboratory.
- Karyotypic abnormality (must display at least 1 metaphase similar/identical to diagnosis; central cytogenetic review by COG required).
- FISH abnormality identical to one present at diagnosis (must be above level of sensitivity of specific FISH probe; central cytogenetic review by COG required).
- PCR or NGS-based demonstration of validated pathogenic leukemogenic lesion (e.g., fusion, mutation) in a CLIA-approved laboratory that matches initial diagnosis and is quantifiable as ≥1%.

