## 11.3.1 CNS Relapse

A single CSF sample with CNS3 status (Rel-CNS3a/b).

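### The leukemia-free survival event cites only the bone marrow relapse criteria, so an isolated extramedullary or CNS relapse is not an event as written

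*Protocol*

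**What the plan says.** Section 13.2.2 defines the LFS event as "event (leukemic relapse [section 11.2] or death from any cause". The Relapse endpoint is "The time to leukemic relapse", with no section cited. Non-relapse mortality (NRM) is "death while in continuous complete remission".

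Section 11.2, Leukemic Relapse, opens with a scope sentence ("Applies to patients who were in remission at the time of transplant", extended to patients who reach remission after transplant). It has one subsection, 11.2.1 Bone Marrow Relapse. Section 11.3 is a separate section at the same level: "Defined as radiographic or biopsy proven extramedullary disease after documented CR or evidence of CSF recurrence". CNS relapse is 11.3.1, beginning with "A single CSF sample with CNS3 status (Rel-CNS3a/b".

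Section 11.2.1 says its criteria follow a COG trial. In the route that needs two tests at 1% or more, the karyotype and FISH examples each carry the condition "central cytogenetic review by COG required". The central laboratory role that this protocol does set up is stated for eligibility: "Multidimensional flow cytometry (MDF) to assess disease status for eligibility will be performed centrally by Hematologics".

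**The concern.** The bracketed reference limits the LFS event to criteria that all require a marrow sample. Suppose a patient in remission has a CSF relapse or a chloroma on Day +120 with a clean marrow. That patient meets 11.3 but, on the text, has no LFS event. The trial admits patients for whom this is realistic: those with past CNS3 disease that has improved (3.2.3) and those with persistent extramedullary disease (3.1.5).

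Twelve-month LFS and relapse at the RP2D are the efficacy measures of secondary objective 1.4(2), and section 2.4 says the trial prepares a full-scale one. Missed or late events can only make LFS look better and relapse look rarer. Two analysts holding the same data could also report different LFS figures, one following the cross-reference and one following common usage.

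The COG condition raises a smaller question of the same kind: whether some marrow relapses can be classified at all under the rules given.

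**Working it through.** No stated design figure depends on this definition, so the main check is of the text.

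**1. Does the cited section reach extramedullary disease?** The three routes in 11.2.1 are a single marrow with at least 5% blasts, a single marrow with at least two tests at 1% or more, and two serial marrows with a one-log rise and the second tests at 0.1% or more. All three are marrow-based. The table of contents also lists 11.2 and 11.3 as siblings, so the numbering is not a text-extraction artefact.

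**2. Do the protocol's other definitions fit that limit?** They do not. Complete remission in 3.1.5 requires at most 1% blasts and no extramedullary disease. Section 11.1 counts persistent extramedullary disease at Day +30 as refractory disease. NRM requires continuous complete remission. Remission therefore ends with an extramedullary relapse, but the LFS event does not occur.

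**3. What happens to one patient with an isolated extramedullary or CNS relapse on Day +120?** Here Relapse is read with the meaning of 11.2.

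| Course up to Day +365 | LFS event | Relapse | NRM | Effect on 12-month LFS |
|---|---|---|---|---|
| Alive, no marrow relapse | none | no | no | raised by 1/20 |
| Marrow relapse follows | at marrow relapse | yes, late | no | none, event delayed |
| Dies without marrow relapse | at death | no | no | none, event delayed |

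In the third row the death is an LFS event that belongs to neither component, so relapse and NRM no longer account for all LFS events.

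**4. Size.** The RP2D cohort is 20 patients (13.3). As a check on that section, the exact 95% interval for 4/20 is 0.057 to 0.437, a width of 0.379, which matches the stated figure. With complete one-year follow-up (assumed), the Kaplan-Meier estimate equals a proportion:

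reported LFS = (x + k)/20

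Here x is the number truly event-free at 12 months, and k is the number with an uncounted extramedullary relapse who are alive and free of marrow relapse then. One case gives 1/20 = 5 points. The values of x and k below are assumptions.

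| x | k = 0 | k = 1 | k = 2 | k = 3 |
|---|---|---|---|---|
| 6 | 30% | 35% | 40% | 45% |
| 8 | 40% | 45% | 50% | 55% |
| 10 | 50% | 55% | 60% | 65% |

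For x = 8, the exact 95% interval moves from 19.1–63.9% at k = 0 to 31.5–76.9% at k = 3.

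**5. The COG condition.** The 5% route accepts FISH confirmation with no COG review. In the two-test route, flow and PCR/NGS carry no such condition, while karyotype and FISH do. The serial route does not mention it. Section 10.3.6 has relapse assessed by institutional guidelines. The research shipments described in section 9 are PK plasma and pre-transplant marrow, and no relapse cytogenetics are sent anywhere. A marrow at 2% by flow, with a matching FISH clone as the only second test, therefore cannot be completed under the two-test route by any step this protocol describes.

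**The case against.** The strongest reply is that the LFS citation is a numbering slip. Section 11.2 has a lone subsection, 11.3 follows directly, and its detailed CNS rules would serve little purpose if they fed no endpoint. In ordinary use, leukemic relapse includes extramedullary relapse. The Relapse endpoint also carries no bracket, so a reader who says it expressly excludes 11.3 goes too far: it is ambiguous, because it borrows the title of 11.2. This is a fair account of the likely intent. It does not rescue the LFS definition, where the reference is explicit and an SAP that follows it would inherit the gap.

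The consequence is also limited. LFS and relapse are secondary and descriptive, with no hypothesis or power, and neither stopping rule in 13.5 uses them. A reader might infer that every isolated extramedullary relapse shifts 12-month LFS by 5 points. It does so only if the patient is alive and free of marrow relapse at 12 months. Section 2.2 describes durable remission after relapse as rare, so some cases would be counted by then anyway. The protocol gives no extramedullary share, so no expected shift can be derived from it.

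On the COG condition, a reader might infer that karyotype or FISH never counts without COG review, or that no such review is available. The text supports neither. The condition sits on two items in one route, the list is headed as examples so another test could serve, and a serial marrow offers a further path. The protocol is silent on arranging the review; it does not say that sites cannot obtain one.

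**Conclusion.** The main point holds. As written, the LFS event omits extramedullary and CNS relapse, against the protocol's own definition of remission, and the Relapse endpoint leaves the matter open. The error has one direction, favourable to the drug. It is worth at most 5 points of 12-month LFS per affected patient, assuming 20 patients with complete one-year follow-up. Against an exact interval about 45 points wide at 8/20 (63.9 − 19.1 = 44.8), a single case is modest. It is nonetheless an avoidable bias, and the definition is the one a later trial would build on.

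The COG point holds only in its narrow form: in the two-test route at 1% or more, the karyotype and FISH examples depend on a central review for which this protocol makes no provision. It bears on marrows from 1% to under 5% blasts that have no other qualifying second test and do not meet the serial route.

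Both points should be corrected. Neither affects the sample size, the primary endpoint or the safety rules.

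**What to change.** 1. In 13.2.2, define the relapse event for both LFS and Relapse as meeting 11.2 or 11.3, including 11.3.1, dated when the criteria are met.
2. State which sample sets the date when an equivocal CNS finding converts to relapse on the repeat CSF one to four weeks later: the initial sample or the confirming one.
3. In the two-test route of 11.2.1, either arrange the COG cytogenetic review or replace the condition with one this trial can meet, such as a named central reviewer or a report from the site's CLIA-approved cytogenetics laboratory showing the abnormality found at diagnosis.

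Items 1 and 2 change wording only. Relapse is already followed to Day +730 in the study calendar. The case report form is not in the document, so check that it records the site and date of relapse. Item 3 is also wording unless the sponsor chooses to set up a review. The price is that reported LFS may be somewhat less favourable.

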# Treatment may not begin without confirmation from the coordinating center that the participant has been registered and enrolled on study.

# 5. TREATMENT PLAN

# 5.1 Treatment Regimen

This is a phase 1/2 trial comprised of a dose-finding phase (phase 1) to determine the RP2D of uproleselan followed by a dose expansion phase (phase 2) to further assess safety and to make a preliminary assessment of efficacy of the RP2D. In both phases, uproleselan will be combined with a high dose busulfan-based myeloablative conditioning regimen (busulfan, fludarabine, and clofarabine) starting with a single dose on day -8, followed by doses q12 hours (H) on conditioning day -7 and ending on day -2 (Table 1).

Table 1. Pre-transplant Conditioning				
Uproleselan with Busu	Uproleselan with Busulfan, Fludarabine, Clofarabine			
Days -8 to day -2	
 
Uproleselan will be administered IV over 20 minutes (+/- 2 minutes) per assigned dose level in the phase 1 portion or at the RP2D in the phase 2 portion. The maximum dose of uproleselan is 800mg BID. The 20 minute infusion time should include the line flush to ensure the full dose has been infused.
 
A single primer dose will be administered on day -8
 
Beginning on day -7 (with start of fludarabine, clofarabine and busulfan) 12 doses of uproleselan will be administered q 12 H.
 
The 1st, 3rd, 5th, and 7th of theses 12 doses (not including initial day -8 dose) should be administered sequentially, after clofarabine and just prior to busulfan. Delay of doses should be avoided.
 
The last dose of uproleselan will be administered 12 hours (+/- 60 minutes) after dose 11.
 
			
Days –7 to –4	Fludarabine 10 mg/m²/dose daily IV administered as a 30 minute*infusion immediately prior to clofarabineClofarabine 30 mg/m²/dose daily IV administered as a 120 minute*infusion immediately after fludarabine and just prior to uproleselanBusulfan IV daily IV over 3 hours administered immediately afteruproleselan.			
	See section 5.2.1 for details			

	• Busulfan exposure targeted to 80-100 mg x h/L		
Day -1	-1 Rest		
Day 0 Hematopoietic Stem Cell Infusion			
*Duration of infusion may be adjusted nor institutional standards			

\*Duration of infusion may be adjusted per institutional standards

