#### 523 Hematopoietic stem cell infusion

The donor graft will be infused on Day 0. Institutional guidelines should be followed for preparation and infusion of grafts.

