## **13.1** Definition of Evaluability

13.1.1 Definition of Evaluability for Dose Escalation Evaluation (Phase 1)

Eligible patients who are evaluable for the dose-determining analysis are those who either: A) meet the following minimum exposure criterion and complete the DLT observation period without experiencing a DLT;

or

B) receive at least 1 dose of uproleselan and experience a DLT during the DLT observation period.

A patient is considered to have met the minimum exposure criterion if he/she received at least 10 of the 12 of planned doses of uproleselan in the first cycle of dosing. Patients who do not meet criteria for inclusion in the dose-determining analysis population will be replaced in the study accrual. 13.1.2 Definition of Evaluability for estimation of efficacy (Phase 2)

Eligible patients will be evaluable for estimation of efficacy if they have received at least one dose of uproleselan at the RP2D. Patients who do not receive any uproleselan will be replaced in the trial accrual.

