#### 13.5 Interim Monitoring Plan

#### 13.51 Monitoring rule for TRM

A one-stage stopping rule will monitor transplant-related mortality (TRM) for the N=20 patients treated at the RP2D. TRM is defined as the occurrence of death from any cause from Day -7 pre-transplant to post-transplant Day +100.

The one-stage interim monitoring rule for TRM is presented in Table 10. If there are 3 or more transplant-related deaths in the 20 patients treated at the RP2D, enrollment to the trial will be suspended so that DSMC can consider terminating the trial. If there are 2 or fewer transplant-related deaths in the 20 patients treated at the RP2D, uproleselan will be declared as safe for further investigation in pediatric patients.

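### A patient who is dosed but never transplanted is in the efficacy set, yet has no defined LFS, OS or NRM time because these run from transplant

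*Protocol*

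**What the plan says.** The protocol fixes both who is analysed and where the clock starts.

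- **Set.** Section 13.1.2: "Eligible patients will be evaluable for estimation of efficacy if they have received at least one dose of uproleselan at the RP2D". Transplant is not a condition. On replacement: "Patients who do not receive any uproleselan will be replaced in the trial accrual". Anyone who has had a dose therefore keeps a place among the 20.
- **First dose.** Table 1 in section 5.1: "A single primer dose will be administered on day -8".
- **Transplant.** Section 5.2.3: "The donor graft will be infused on Day 0".
- **Clock.** Section 13.2.2 gives OS as "The time from transplant to death from any cause, or censored on date of last contact, if no death occurs". For NRM the wording is "The time from transplant to death while in continuous complete remission, or censored on date of last contact, if no death occurs". LFS has the same start, with relapse or death as the event.
- **Curves.** Section 13.7 applies the Kaplan-Meier method to patients treated at the recommended phase 2 dose (RP2D), not to transplanted patients, and reads off 1-year LFS, OS and NRM.
- **TRM.** Section 13.51 uses a third start point: "TRM is defined as the occurrence of death from any cause from Day -7 pre-transplant to post-transplant Day +100".

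Section 5.5 keeps patients on study after they leave protocol therapy. Section 5.6 counts the two years of follow-up from the day of transplantation.

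**The concern.** Eight days separate the dose that admits a patient to the efficacy set from the event that starts the survival clock. A patient who dies in that interval, or whose transplant is cancelled, belongs to the analysed cohort but has no time from transplant. Nothing in the protocol says how that patient enters the curves.

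The case is not far-fetched on the protocol's own terms. The TRM window opens before transplant, so deaths during conditioning are foreseen. The off-therapy criteria in section 5.5 are not limited to the period after Day 0.

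At stake are 12-month LFS and OS, the stated measures of preliminary efficacy in section 1.4. The exploratory summaries in section 13.8 are also affected, because they classify the same cohort by LFS status one year after transplant. A pre-transplant death is the earliest possible failure, and omitting it flatters the result. The same death could count toward the TRM rule and be missing from OS.

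**Working it through.** **1. The plan's own figures.** Section 13.3 states an exact 95% confidence interval width of 0.379 for an observed 0.20 in 20 patients. The Clopper-Pearson interval for 4/20 is 0.0573 to 0.4366, width 0.3793, so the figure reproduces. The TRM rule (2 or fewer deaths of 20 is acceptable) gives P(X ≤ 2) = 0.0913 at P = 0.25 and 0.9245 at P = 0.05, matching the stated 9.1% and 92.5%. Neither calculation uses a time origin, so this point changes neither figure.

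**2. Where a death is counted, by day.**

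| Day of death | In 13.1.2 set | TRM (from Day -7) | OS and LFS (from Day 0) |
|---|---|---|---|
| Day -8, after the priming dose | yes | outside window | no defined time |
| Day -7 to Day -1 | yes | counted | no defined time |
| Day 0 to Day +100 | yes | counted | counted |

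**3. Effect of leaving out deaths before Day 0.** Inputs: N = 20 from section 13.3. The number k of pre-transplant deaths and the number alive at 12 months are assumptions, because the documents give neither. Censoring before 12 months is ignored, so the estimate is a simple proportion. With all k patients dead, the all-treated estimate is a/20 and the estimate with them left out is a/(20 − k).

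| k left out | OS, a = 12 | LFS, a = 8 |
|---|---|---|
| 0 | 12/20 = 60.0% | 8/20 = 40.0% |
| 1 | 12/19 = 63.2% | 8/19 = 42.1% |
| 2 | 12/18 = 66.7% | 8/18 = 44.4% |
| 3 | 12/17 = 70.6% | 8/17 = 47.1% |

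One omitted death shifts the estimate by about 2 to 3 points, and three shift it by about 7 to 11.

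**4. Cancelled transplant, patient alive at 12 months.** Suppose 12 of 19 transplanted patients and the one untransplanted patient are alive. All treated: 13/20 = 65.0%. Untransplanted patient left out: 12/19 = 63.2%. OS is now too low, so the direction depends on what later happens to the patient.

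**5. Scale.** For 12/20 the exact 95% interval is 0.361 to 0.809, width 0.448. A shift of 3 points is small beside it.

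**The case against.** Transplant is a usual origin in this field, and it suits a protocol whose hypothesis concerns relapse after transplant. The endpoints are secondary and descriptive. A reader might infer four stronger things that the documents do not support.

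- *The patient is dropped from the curves.* No section says so. It is the natural result of an undefined time, but an analyst could enter a pre-transplant death as an event at time zero. For deaths, the set and the origin are therefore not strictly irreconcilable.
- *Stopping uproleselan before Day 0 is enough to lose the patient.* It is not. A patient who stops early but receives the graft has a valid time from transplant. Only a patient who is never transplanted is affected.
- *The bias is always upward.* This is certain only for deaths left out.
- *A Day -8 death goes unnoticed.* It would still be in the safety set (13.1.3), reported as a serious event (7.4 and 7.5) and seen by the monitoring committee (12.2). Only the TRM rule and the survival endpoints miss it.

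It is also fair to say that TRM is a monitoring rule with its own purpose and need not share a window with OS, and that a statistical analysis plan might supply a handling rule. The narrower point stands. A transplant origin is coherent when the analysed set is transplanted patients, and sections 13.1.2 and 13.7 define the set differently. This is a misfit between two things the protocol does state, not a detail left for later.

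**Conclusion.** The point holds for patients who are dosed and never transplanted. They are evaluable, they are not replaced, and section 13.2.2 gives them no LFS, OS or NRM time. If such patients die before Day 0 and are left out, 12-month OS and LFS are biased upward by about 2 to 3 points per patient at N = 20. That size rests on assumed survivor counts of 8 or 12 and on no censoring. For cancelled transplants the direction is open.

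The documents give no pre-transplant loss rate, and the event is probably uncommon. No sample-size, power or precision figure is affected. This is a minor correction, best made before anyone knows which patients it touches.

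**What to change.** - **Section 13.2.2.** Measure OS and LFS from the first dose of uproleselan for every patient in the 13.1.2 set, and count deaths before transplant as events.
- **Section 13.51.** Start the TRM window at the first dose, so that a death on Day -8 after that dose is counted.
- **Section 5.6.** State that untransplanted patients are followed for survival, and from what date.
- **NRM, relapse and engraftment.** Keep these from transplant, in transplanted patients. NRM should not move to Day -8, because it requires remission at death and section 3.1.5 admits refractory patients.
- **Reporting.** Give the number and outcome of dosed but untransplanted patients separately. LFS and OS from Day 0 in transplanted patients can stay as a supporting summary for comparison with historical series.

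The cost is wording. Infusion times are already recorded under section 9.1. OS and LFS times lengthen by about 8 days relative to the usual transplant origin. One further sentence is needed: section 11.2 ties leukemic relapse to remission status at transplant or at the Day +30 assessment, so the amendment must say how LFS is scored for a patient who is alive and untransplanted.
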